5.4.2 Supportive secondary endpoint(s)

Not applicable no supportive secondary analysis is planned for this study.

5.5 Exploratory Endpoint(s) Analysis

Exploratory endpoints related to the comparison of PK and PD parameters are covered under [section 5.4](#).

5.5.1 Immunogenicity Analyses

The development of antidrug antibodies during the study will be evaluated to assess the immunogenicity potential of the study drug.

The anti-drug (rozanolixizumab) antibody (ADA) screening status (positive or negative screen), confirmatory status (positive or negative immunodepletion), and the titer for “positive immunodepletion” samples at each scheduled assessment during the In-Clinic and SFU Periods will be presented.

The results of the ADA analyses will be listed and summarized by cohort treatment group (refer [section 5.1.1.3](#)) and time point for the SS.

Anti-drug antibodies will be measured using a three-tiered assay approach: screening assay, confirmatory assay and titration assay. All immunological analyses will be exploratory.

Samples will first be evaluated in the screening assay using a false positivity rate of 5% (reported as ‘negative screen’ or ‘positive screen’), followed by analysis of screened positive samples in the confirmatory assay (which is a drug depletion assay) to confirm the true positivity of the samples (reported as ‘negative immunodepletion’ or ‘positive immunodepletion’). Samples that are confirmed as positive will be evaluated in a titration assay to quantify the ADA level and will be reported as titer (reciprocal dilution factor including minimum required dilution (MRD)).

The ADA status should be determined for each visit where samples were taken for ADA analysis.

- Sample values that are either ‘negative screen’ or ‘positive screen’ and ‘negative immune depletion’ will be defined as ADA negative.
- Sample values that are ‘positive screen’ and ‘positive immune depletion’ will be defined as ADA positive.

In addition, the anti-drug antibody status will be further classified based on participant levels as outlined below. This classification should be done for entire study duration (i.e. the treatment period including SFU sampling time point).

1. **Pre ADA negative – treatment induced ADA negative:** Includes participants who are negative at Baseline and antibody negative at all sampling points post treatment. This group also includes participants who have a missing pretreatment sample (either missing or insufficient volume) at Baseline with all ADA post-treatment samples negative.
2. **Pre ADA negative – treatment induced ADA positive:** Includes participants who are negative at Baseline and antibody positive at any sampling point post treatment. This group also includes participants who have a missing pretreatment sample (either missing or insufficient volume) at Baseline with one or more ADA positive post-treatment samples.
3. **Pre ADA positive – treatment reduced ADA:** Includes participants who are positive at Baseline, and antibody negative at all sampling points post treatment.
4. **Pre ADA positive – treatment unaffected ADA:** Includes participants who are positive at Baseline and are positive at any sampling point post treatment with titer values of the same magnitude as Baseline (ie, less than a predefined fold difference increase from the Baseline value, i.e. the minimum significant ratio (MSR) determined during assay validation).
5. **Pre ADA positive – treatment boosted ADA positive:** Includes participants who are positive at Baseline and are positive at any sampling point post treatment with increased titer values compared to Baseline (greater than a predefined fold difference increase from Baseline value, i.e. the MSR determined during assay validation).
6. **Inconclusive:** Includes participants who have a positive or negative pretreatment sample and at least one post-treatment samples are missing, while other post-treatment samples are ADA negative.

Based on the overall ADA participant classification above, the following will be determined and presented in tables:

- Total prevalence of pre-Antibody: n/N % number of participants that are pre ADA positive, i.e. from categories 3, 4, 5.
- Total incidence of treatment-emergent ADA positive: n/N % number of participants in category 2 and category 5.

The following summaries, figures and listings will be produced and will be presented:

-
- Summary table displaying the number and percentage of participants with a positive ADA status and negative ADA at the time of each visit by cohort and treatment group.
 - Summary tables displaying the number and percentage of participant in each of the ADA participant categories (1 – 6), total prevalence of pre-Antibody and total incidence of treatment-emergent ADA positivity as defined above by cohort treatment group.

Spaghetti plots of ADA titer (y-axis) by visit (x-axis). This plot will include the following ADA participant categories:

- a) Category 2: Pre ADA negative – treatment-induced ADA positive
- b) Category 4: Pre ADA positive – treatment unaffected ADA positive
- c) Category 5: Pre ADA positive – treatment-boosted ADA positive

All categories will be presented on the same plot (visualized using different colors). Plots will be presented using a semi-logarithmic scale for the ADA titers (ADA negative samples will therefore be excluded from the plot).

A listing of anti-rozanolixizumab antibodies will include all derived results.

Serum complement (C3, C4) and cytokines and plasma complement (C3a, C5a)

Listing will be provided for serum complement (C3, C4) and cytokines and plasma complement sampling details (C3a, C5a).

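### Prevalence of pre-existing ADA omits baseline-positive participants classed as inconclusive; separately, categories 4 and 5 need a precedence rule

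*SAP*

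**What the plan says.** SAP 5.5.1 classifies each participant over the whole study. For those positive at baseline the relevant categories are:

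- Category 3 (reduced): "positive at Baseline, and antibody negative at all sampling points post treatment".
- Category 4 (unaffected): "positive at any sampling point post treatment with titer values of the same magnitude as Baseline", explained as "less than a predefined fold difference increase from the Baseline value", where the fold difference is the minimum significant ratio (MSR) from assay validation.
- Category 5 (boosted): "positive at any sampling point post treatment with increased titer values compared to Baseline", explained as "greater than a predefined fold difference increase from Baseline value", again the MSR.
- Category 6 (inconclusive): "a positive or negative pretreatment sample and at least one post-treatment samples are missing, while other post-treatment samples are ADA negative".

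Two rates follow. Prevalence of pre-existing antibody is the "number of participants that are pre ADA positive, i.e. from categories 3, 4, 5". Incidence of treatment-emergent ADA is taken from categories 2 and 5.

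The same section also plans a table of ADA-positive and ADA-negative participants at each visit, a table of counts in all six categories, and a listing of all derived results. It calls all immunological analyses exploratory. SAP 5.3.2 uses treatment-emergent ADA status to split one of the TEAE tables.

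**The concern.** The prevalence definition equates two sets that differ. Being ADA positive predose is a fact about one sample. Membership of categories 3, 4 or 5 also depends on what was collected after dosing. Category 6 names participants with a positive predose sample, so the SAP itself places some known baseline positives outside the three categories that it counts. With the denominator held at the group size, which is the general rule for percentages in SAP 5.1, the omission can only lower the result.

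At stake is a descriptive baseline figure in very small groups, where one person matters. It could also disagree with the predose row of the by-visit table in the same report.

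A smaller matter is that categories 4 and 5 both turn on any post-dose sample. A participant with one unchanged and one boosted titer satisfies both, and a rise exactly equal to the MSR satisfies neither. The six-category table and the titer plot colored by category need one category per person, and the SAP gives no rule for choosing.

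**Working it through.** The plan states no ADA rate, so there is no figure to reproduce. The check is of the definitions, then of size.

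**Inputs.** One predose and four post-dose ADA samples, on Days 10, 16, 22 and 57 (Protocol Table 1-1, footnote u). Six active participants per cohort, 24 in all (Protocol 7.2), hence 12 per method. Category definitions from SAP 5.5.1.

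**Step 1: trace one participant.** Predose positive; Day 10 negative; Day 16 missing; Days 22 and 57 negative. Category 3 fails, because not every point is negative. Categories 4 and 5 fail, because no post-dose sample is positive. Category 6 applies. The participant is outside the prevalence numerator but counts as positive in the predose row of the by-visit table.

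**Step 2: how narrow the condition is.** Let each post-dose sample be negative, positive with a rise below, equal to or above the MSR, or missing. That gives 5^4 = 625 patterns for a baseline positive. These are logical cases, not probabilities.

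- Category 6: every sample negative or missing, at least one missing: 2^4 − 1 = 15.
- With exactly one sample missing there are 4 × 4^3 = 256 patterns. Only 4 go to category 6 (the other three samples all negative). In 224 the participant meets category 4, 5 or both and stays in the prevalence count. The other 28 meet no category because of the MSR boundary.

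So a missing sample removes a baseline positive through category 6 only when every other post-dose sample is negative.

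**Step 3: size per participant.** 1/6 = 16.7 points in an active cohort; 1/12 = 8.3 points per method. Example: 2 of 6 positive predose, one of them in category 6, gives 2/6 = 33.3% by predose status and 1/6 = 16.7% by the SAP rule.

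**Step 4: how often (assumed rates).** If each sample is missing independently with probability m, a baseline positive who would otherwise be negative throughout enters category 6 with probability 1 − (1 − m)^4:

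- m = 3%: 0.115 (about 11%)
- m = 5%: 0.185 (about 19%)
- m = 10%: 0.344 (34%)

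Let p be baseline positivity and r the share of baseline positives otherwise negative post-dose. Then q = p × r × [1 − (1 − m)^4], and the chance that at least one of 24 active participants is dropped is 1 − (1 − q)^24.

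- Low end, p = 2%, m = 2%, r = 25%: 0.009, about 1%.
- High end, p = 10%, m = 10%, r = 100%: 0.568, about 57%.

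The expected number dropped with r = 100% is 24 × 0.05 × 0.185 = 0.2 at p = m = 5%, and 24 × 0.10 × 0.344 = 0.8 at p = m = 10%.

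**Step 5: categories 4 and 5.** Of the 625 patterns, 625 − 2 × 4^4 + 3^4 = 194 meet both; with complete data it is 110 of 256. A further 3^4 − 2^4 = 65 meet neither, nor any other category, because every positive sample sits exactly at the MSR. Prevalence counts both categories, so the overlap leaves it unchanged when each person is counted once. Incidence counts everyone meeting category 5, so it equals the result under a rule that puts 5 before 4. It falls only if a programmer places a dual-qualifying participant in category 4.

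**The case against.** The strongest reply is that little is lost. The analyses are exploratory and SAP section 2 plans no hypothesis tests. The by-visit table and the listing show predose status, so a reader can recover the right figure. Missing samples are also limited: Protocol 8.9.1 asks for an ADA sample at withdrawal, SAP 5.1.1.1.3 maps early-discontinuation results to a scheduled visit, and Protocol 7.2 allows replacement. The expected number of affected participants is below one under the rates in Step 4. All of this stands and sets the severity. It does not make the prevalence formula right, and recovering the figure from another table means that the report contains two.

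It could also be argued that category 3 covers these participants if all sampling points means all available ones. That would put them in categories 3 and 6 together, and category 6 would have had no need to name positive predose samples.

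A reader might infer more than the documents support:

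- That any single missed post-dose sample removes a baseline positive. It does not; the other samples must all be negative (Step 2).
- That the 4/5 overlap makes the ADA rates wrong by construction. Read literally, it changes neither rate (Step 5). It is a missing precedence rule.
- That the MSR boundary will lose participants. Titers are reciprocal dilution factors, so equality is possible, but whether it can occur depends on the dilution series and the MSR, and neither is given.

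**Conclusion.** The point holds for prevalence. As defined, prevalence of pre-existing ADA leaves out baseline positives in category 6 and is understated whenever one occurs, by 16.7 points per person in an active cohort of 6 and 8.3 points in a method group of 12. This follows from the SAP text alone, with the group size as denominator.

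How likely it is does not follow from the documents. The 11%, 19% and 34% figures assume independent missingness of 3%, 5% and 10% per sample and apply only to baseline positives who are otherwise negative after dosing; they are not errors in the reported rate. The 1% to 57% range rests on assumed positivity, missingness and post-dose behavior.

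The lack of a rule between categories 4 and 5 is an ambiguity worth closing, because treatment-emergent status also feeds a TEAE table. It is not an error in either rate. Overall this is a minor improvement: no primary or secondary endpoint uses these categories.

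**What to change.** In SAP 5.5.1:

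1. Define prevalence of pre-existing ADA as participants with a positive predose sample divided by participants with a valid predose sample, whatever their post-dose category. This also fixes N for that rate and removes participants with no predose result, whom categories 1 and 2 treat as negative, from its denominator.
2. State that a baseline-positive participant with any post-dose titer exceeding the MSR-fold increase is category 5, and that every other baseline positive with a post-dose positive is category 4. This keeps the SAP's strict inequality for category 5, assigns a rise equal to the MSR to category 4, and gives each such participant one category.

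Category 6 can stay as it is for describing post-dose response. The cost is two sentences and minor programming, with no new data. SAP section 1 requires an amendment for changed definitions before database lock; making the change before unblinding avoids a choice made with results in view.

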5.5.2 Exploratory Analyses on the effect of rozanolixizumab on infection specific IgG

Observed values at baseline and at SFU and change from Baseline to SFU in IgG concentrations will be summarized descriptively for each treatment group for the following virus specific IgG concentrations

Tetanus specific IgG

Influenza A virus-specific IgG antibodies,

SARS Cov-2 antibodies for COVID-19 vaccinated and/or previously infected participants

For SARS-COV-2 antibodies, the summary table will present one row for vaccinated participants, a second row for previously infected participants, and a final row for those with both (if any). In addition to the summary table, the data for the above specific antibodies will be listed for all the collected timepoints.

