**Table 1-1: Schedule of activities**

Assessments	Screening Period	In-Clinic Period										Ambulatory Period									
		Admission	Dosing																	SFU/WD	
			Weeks	-4 to -1	0	1										1	2	2	3		3
Days	-28 to -2	-1 a	1				2	3	4	5 b	7	10	13	16	19	22	29	43	57		
Hours			0	4	6	8	12	24	48	72	96										
Informed consent	X																				
Inclusion/exclusion criteria	X	X																			
Randomization c			X																		
IMP administration d			■																		
Demography	X																				
Prior and concomitant medications	X	X	X	X	X	X	X	X	X	X	X	X	X	X	X	X	X	X	X		
SARS-CoV-2 testing (PCR)	X	X									X								X		
Influenza, tetanus, and SARS-CoV-2 antibody assessment	X	X									X								X		
Study participant card e			X																		
Medical/procedure history	X																				
Physical examination f	X	X									X								X		
Pregnancy test g	X	X															X		X		
Serum FSH level h	X																				
Tuberculosis test and questionnaire	X																				
Alcohol urine test and urine drug screen	X	X																			

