**Table 1-1: Schedule of activities**

Assessments	Screening Period	In-Clinic Period										Ambulatory Period									
		Admission	Dosing																	SFU/WD	
Weeks	-4 to -1	0	1										1	2	2	3	3	4	5	7	8
Days	-28 to -2	-1 a	1					2	3	4	5 b	7	10	13	16	19	22	29	43	57	
Hours			0	4	6	8	12	24	48	72	96										
Anti-rozanolixizumab antibodies u			X										X		X		X		X		
Headache questionnaire f			X	X	X	X	X	X	X	X	X	X									
Neurological assessment s			X	X	X	X	X	X	X	X	X										
Serum complement (C3, C4), and cytokines and plasma complement (C3a, C5a) t			X																		

AE=adverse event; CSF=cerebrospinal fluid; CT=computed tomography; ECG=electrocardiogram; FSH=follicle-stimulating hormone; IgG=immunoglobulin G; IMP=investigational medicinal product; ISRQ=injection site reaction questionnaire; MP>manual push; PCR=polymerase chain reaction; PK=pharmacokinetic(s); SARS-CoV-2=severe acute respiratory syndrome coronavirus 2; SC=subcutaneous(ly); SFU=Safety Follow-Up; SIAQ=self-injection assessment questionnaire; VAS=visual analog scale; WD=withdrawal

a Participants may be admitted into the clinic in the evening of Day -2 for the In-Clinic Period.

b Participants discharged during Day 5 at the discretion of principal investigator.

c Randomization should be performed on Day 1 before dosing and after all predose assessments and procedures have been completed.

d Rozanolixizumab will be administered as an SC infusion by syringe driver at a [REDACTED] or by MP through self-administration at a [REDACTED]

e This card is an emergency contact card and will be given to the participant when he/she is randomized in the clinical study (Day 1).

f A full physical examination will be performed at the Screening Visit, Day -1, and SFU. A brief symptom-led physical examination should be performed on Day 5.

g Serum pregnancy tests will be performed at the Screening Visit and on Day -1 and 29 and at the SFU Visit for all women with childbearing potential.

h Only for postmenopausal women (for at least 1 year post-menopause before the Screening Visit) not using hormonal contraception or hormonal replacement therapy.

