In UP0060, [REDACTED]-dose SC administration of rozanolixizumab to healthy Japanese, Chinese, and Caucasian study participants was generally well tolerated with an acceptable safety profile after [REDACTED] SC administration of [REDACTED] doses. Overall, patterns in the incidence of TEAEs observed in Japanese and Chinese study participants were generally comparable to those observed in Caucasian participants. In all study participants, a numerically higher incidence of TEAEs was reported for study participants receiving rozanolixizumab (38 participants [77.6%] reported 115 TEAEs) compared with placebo (10 participants [62.5%] reported 23 TEAEs). Among participants receiving rozanolixizumab, there was a trend towards increased incidence of TEAEs with higher doses (55.6%, 75.0%, and 90.0% of participants in the rozanolixizumab [REDACTED] dose groups, respectively). Three participants (6.1%) reported 4 TEAEs of special monitoring (diarrhea [2 events], abdominal pain [1 event], and vomiting [1 event]) in the [REDACTED] cohort, all of moderate intensity. The [REDACTED] dose was concluded by the investigator to be not well tolerated by 1 Caucasian volunteer who reported moderate headache. Dose-dependent reductions in IgG and IgG subclasses, similar to that observed in UP0018, were seen following administration of rozanolixizumab in all 3 ethnicities. Tetanus- and influenza A virus-specific IgG concentrations over time were similar to total IgG following the administration of rozanolixizumab, generally reaching the lowest levels around Day 10 and returning close to Baseline by Day 57; the geometric mean concentrations for tetanus- and influenza A virus-specific antibodies generally remained at acceptable levels for

protection time in all ethnic and dose groups. Overall, the mean value of albumin remained within the normal range over time, and no clinically relevant changes from Baseline were observed. All injection site reactions observed for rozanolixizumab were self-limiting, short-term, and of mild intensity.

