**Table 3-1: Study objectives and endpoints**

Objectives	Endpoints/Estimands

 
To evaluate the effects of rozanolixizumab on the concentrations of IgG on tetanus, influenza A virus-specific IgG antibody, and COVID-19 vaccinated/previously infected participants
 
	
 
Values and change from Baseline in serum IgG concentrations at each scheduled assessment during the In-Clinic and SFU Periods
 
Values and change from Baseline in tetanus, influenza A virus-specific IgG antibodies, and COVID-19 vaccinated/previously infected participants during the In-Clinic and SFU Periods
 

 
To assess total volume, total time, and infusion rate for MP and syringe driver
 
	
 
Volume of IMP administration
 
Time from start to completion and resultant infusion rate of IMP administration
 
Time of infusion setup for both modes of administration
 

 
To assess acceptability of SC rozanolixizumab administration by MP vs syringe driver
 
	
 
Postdose infusion site pain visual analog scale with IMP administration
 

 
To assess the experience with SC infusions
 
	
 
Pre- and postdose SIAQ for MP administration
 
Postdose ISRQ for syringe driver administration
 

Other Safety	

 
To evaluate changes from Baseline in vital signs, 12-lead electrocardiogram, and laboratory measurements following [REDACTED] doses of rozanolixizumab administered by SC MP vs syringe driver in healthy study participants
 
	
 
Vital signs measurements (blood pressure, pulse rate, respiratory rate, and body temperature), 12-lead electrocardiogram, and local tolerability assessments at each scheduled assessment during the In-Clinic and SFU Periods
 
Changes from Baseline in clinical laboratory assessments will consist of hematology including coagulation, clinical chemistry, and urinalysis at each scheduled assessment during the In-Clinic and SFU Periods
 

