5.1.1.1.2 Study periods

The following study periods are defined:

Pre-treatment Period: This period is defined as the period prior to the date of first dose of IMP. The period ends at the day prior to the date of IMP administration.

In-Clinic Period: This period starts at the date of first dose of IMP (Day 1) and ends on the date of discharged from the clinical study center (Day 5).

Ambulatory Safety Follow-Up Period: This period starts at the day after the date of discharge (Day 5) and ends at study completion (i.e. Day 6 through Day 57).

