The geometric least square mean (GLSM), GLSM differences and the corresponding 90% CI for the differences (MP [Test] - syringe driver [Reference]) will be calculated for PK parameters (log-transformed C_{max} , AUC_{0-t}). Back-transformed (anti-log) estimates of (GLSM, geometric least square mean ratio (GLSMR) and its 90% CI for the comparisons will be presented. In order to verify the normality assumption of the ANOVA, normal quantile-quantile plots will be used to visually inspect the distribution of residuals, and the potential impact of any deviations will be discussed.

PD analyses

All PD summaries will be done using PD-PPS by treatment group described under [section 5.1.1.3](#). Total IgG (observed values, change from Baseline, and percentage change from Baseline) will be listed and summarized for the PD Per Protocol Set. The geometric mean Total IgG concentration with 95% CI will be displayed graphically.

Derived parameters for the Total IgG response curve (AUC, maximum decrease in total plasma IgG, and time to minimum plasma concentration) will be listed and summarized for the PD Per Protocol Set.

The comparability of the total dose adjusted IgG Baseline-corrected AUC (IgG)/D between MP and the syringe driver will be assessed within an ANCOVA model with Baseline IgG value fitted as a covariate. The least square mean (LSM), LSM differences and the corresponding 95% CI for

the differences will be presented for total IgG. The analysis may be conducted on the log scale if the data exhibits substantial non-normality. In this case, the reason for the log-transformation will be described.

The following contrasts will be presented:

- Rozanolixizumab via Syringe Driver vs Rozanoliximab via MP
- Placebo via Syringe Driver vs Placebo via MP
- Rozanolixizumab via Syringe Driver vs Placebo via Syringe Driver
- Rozanoliximab via MP vs Placebo via MP

Additionally, observed values and change from Baseline in serum IgG concentrations at each scheduled assessment during the In-Clinic and SFU Periods will be summarized descriptively.

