6.2 Appendix 2: Changes to Protocol-Planned Analyses

As per protocol “All safety variables will be analyzed by descriptive methods and presented by treatment (rozanolixizumab or placebo), method (MP or syringe driver), body weight, and dose level.” However, the analysis were planned by cohort and treatment group as per the SAP section [5.1.1.3](#). All other analysis were planned as per the protocol.

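### The planned summary of tetanus, influenza A and SARS-CoV-2 antibodies skips Day 5, their only postdose sample in the In-Clinic Period, and SAP 6.2 does not declare it.

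*SAP*

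**What the plan says.** Protocol Table 3-1, repeated in SAP Table 1-1, defines the exploratory endpoint as: "Values and change from Baseline in tetanus, influenza A virus-specific IgG antibodies, and COVID-19 vaccinated/previously infected participants during the In-Clinic and SFU Periods". Protocol Table 1-1 schedules the samples in the row "Influenza, tetanus, and SARS-CoV-2 antibody assessment", with marks at Screening, Day -1, Day 5 (96 hours) and SFU (Day 57).

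SAP 5.1.1.1.2 starts the In-Clinic Period on Day 1 and says that it "ends on the date of discharged from the clinical study center (Day 5").

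For the analysis, SAP 5.5.2 says: "Observed values at baseline and at SFU and change from Baseline to SFU in IgG concentrations will be summarized descriptively for each treatment group". It adds a listing of the antibody data at every time point collected. SAP 6.2 declares one change from the protocol, the grouping used for safety variables, and then says: "All other analysis were planned as per the protocol".

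For total IgG, a separate endpoint under the same objective, SAP 5.4.1.2 says: "observed values and change from Baseline in serum IgG concentrations at each scheduled assessment during the In-Clinic and SFU Periods will be summarized descriptively".

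**The concern.** The endpoint spans two periods, but the summary covers a postdose value from only one of them. The choice of period matters because of the expected time course. Protocol 2.2 reports that in UP0060 the tetanus and influenza A antibodies followed total IgG, "generally reaching the lowest levels around Day 10 and returning close to Baseline by Day 57".

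A table of Baseline, Day 57 and the change between them therefore looks mainly at the point where levels should have recovered. The objective is to evaluate what rozanolixizumab does to these antibodies. A near-zero change at Day 57, shown alone, could be read as no effect when it may only mean that the effect has passed. Day 5 is the only scheduled sample between dosing and Day 57, so it offers the only group-level estimate for these antibodies while a reduction is expected.

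**Working it through.** No test, error rate or sample-size figure is involved. The check compares the schedule, the endpoint and the planned table, and then counts.

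**1. Which days are sampled.** Columns in Table 1-1 are easy to misalign, so I checked the marks against footnoted rows.
- The antibody row has the same mark positions as the physical examination row. Footnote f places that row at Screening, Day -1, Day 5 and SFU, and says of the third mark: "A brief symptom-led physical examination should be performed on Day 5". The third mark also falls under 96 hours, which the header equates with Day 5.
- The last mark is in the same column as the last mark of the anti-rozanolixizumab antibody row, which footnote u fixes as Day 57.

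The samples are therefore two predose (Screening, Day -1) and two postdose (Day 5, Day 57).

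**2. Which period each postdose sample belongs to.** Under SAP 5.1.1.1.2, Day 5 falls in the In-Clinic Period and Day 57 in the follow-up period. The protocol starts its In-Clinic Period at admission, so a Day -1 value could also count as in clinic. That value is predose, however, and a change from Baseline needs a postdose value. Day 5 is the only one in that period.

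**3. Coverage of the planned table.**

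| | Scheduled | Summarised in SAP 5.5.2 |
|---|---|---|
| Postdose time points | 2 (Day 5, Day 57) | 1 (Day 57) |
| Postdose time points, In-Clinic Period | 1 (Day 5) | 0 |

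**4. Values affected**, assuming full enrolment and no missed samples.
- Participants: 4 cohorts × (6 + 2) = 32, of whom 4 × 6 = 24 receive rozanolixizumab and 4 × 2 = 8 placebo.
- Tetanus and influenza A at Day 5: 32 × 2 = 64 values, made up of 24 × 2 = 48 active and 8 × 2 = 16 placebo.
- SARS-CoV-2 at Day 5: one value per vaccinated or previously infected participant. The documents do not give that number, so the range is 0 to 32.

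**5. What a Day 5 row could display under SAP 5.1.** Groups with n below 3 show only n, minimum and maximum, which applies to placebo within a cohort (n = 2). By administration method, placebo has 2 × 2 = 4 and rozanolixizumab 6 × 2 = 12, and both get the full set of statistics. For tetanus and influenza A, a Day 5 row would thus be informative in the by-method groupings.

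**6. Declaration.** Nothing in SAP 6.2 mentions these antibodies, and its closing sentence says that the remaining analyses follow the protocol. For this endpoint, as Table 3-1 words it, they do not.

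**The case against.** The other side has several fair points.

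- **The endpoint wordings differ.** The total IgG endpoint asks for each scheduled assessment. The specific-antibody endpoint names only the two periods and no visit. This stands, and it weakens the contrast with SAP 5.4.1.2 as evidence of inconsistency. It does not remove the In-Clinic Period from the antibody endpoint, and Day 5 is the only postdose sample that can serve it.
- **Protocol Section 9 sets out no specific analysis for these antibodies**, so it can be argued that no planned analysis was changed. The gap is indeed between endpoint and analysis. But the endpoint stands in the SAP's own Table 1-1 as well as in the protocol, and SAP 6.2 gives an unqualified assurance.
- **Day 5 is listed.** This is true, and no data are lost. However, protocol 9.2 makes listings additional to summaries, and the SAP 5.5.2 listing does not promise a Day 5 change from Baseline or any group-level figure.
- **SAP 5.1 already provides summaries by day.** It does so only where applicable, and SAP 5.5.2 is the specific rule with its time points named. A programmer would follow 5.5.2.
- **Total IgG will show the fall, including at Day 10, and Day 5 is not the expected low.** Both statements are correct. The documents give no Day 5 effect size for the specific antibodies, so how much a Day 5 row would reveal is unknown. Total IgG still does not answer a separately stated endpoint.

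**Conclusion.** The concern holds. Followed as written, the SAP produces a group table for these antibodies whose only postdose point is Day 57. It covers 1 of 2 scheduled postdose samples and none of the postdose in-clinic data, and the departure is undeclared. At full enrolment, 64 tetanus and influenza A values at Day 5, and up to 32 SARS-CoV-2 values, would be listed without a group summary.

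The consequence is limited. The endpoint is exploratory and descriptive, no hypothesis is tested, and the primary and secondary endpoints are unaffected. The change should be made because it is cheap and bears directly on whether the table can answer its own objective.

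The conclusion about coverage rests on the reading of Table 1-1 confirmed by its footnotes. The conclusion about what Day 57 can show assumes that the UP0060 time course carries over. For SARS-CoV-2 antibodies a similar course is only inferred.

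**What to change.** Amend SAP 5.5.2 so that observed values are summarised at Baseline, Day 5 and SFU, and change from Baseline at Day 5 and SFU, using the by-cohort and by-method treatment groupings already in SAP 5.1. State in the study report that the low expected around Day 10 is not sampled for these antibodies, so that Day 5 is not taken for the maximum reduction. If Day 5 was left out on purpose, record that and the reason in SAP 6.2 instead.

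The cost is one more time point in a planned table and a short SAP amendment, which SAP Section 1 requires when analysis definitions change before database lock. The Day 5 samples are already scheduled and listed, so no protocol amendment or extra blood is needed.
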